4.4 Early Withdrawal of Subjects

4.4.1 When and How to Withdraw Subjects

Patients are free to withdraw at any time and for whatever reason. No data will be collected for withdrawn subjects and withdrawn subjects will not be replaced. There will be no follow-up for withdrawn subjects. Pre-specified reasons for discontinuing include, but are not limited to, the following:

- Patient request: Patient decided that he/she did not want to continue (for any reason).
- •Adverse Event: Patient experienced a related or unrelated event that would interfere with the study objectives/evaluation
- •Lost to Follow-up: Patient did not come in for a visit and could not be reached by phone
- Treatment Failure: If in the Principal Investigator's judgment, the patient's condition required another form of treatment
- •Noncompliance: Patient is not complying with the protocol requirements (i.e. visit schedule, dosing, regimen, etc.); a patient is to be withdrawn if he/she misses two consecutive visits
- •Other: Any other reason

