4.4.2 Data Collection and Follow-up for Withdrawn Subjects

If a Participant withdraws from the study, no additional attempts will be made to contact the Participant.

5 Study Drug

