For this study, the study treatment follow-up period is defined as the last scheduled visit.

Preexisting condition

A preexisting condition is one that is present at the start of the study. A preexisting condition should be recorded as an adverse event if the frequency, intensity, or the character of the condition worsens during the study period.

General Physical Examination Findings

At screening, any clinically significant abnormality should be recorded as a preexisting condition. At the end of the study, any new clinically significant findings/abnormalities that meet the definition of an adverse event must also be recorded and documented as an adverse event.

Post-study Adverse Event

All unresolved adverse events are to be followed by the Principal Investigator and/or Investigators until the events are resolved, the subject is lost to follow-up, or the adverse event is otherwise explained. At the last scheduled visit, the Principal Investigator and/or Investigators should instruct each subject to report and any subsequent event(s) that the Participant, or the Participant's personal physician, believes might reasonably be related to participation in this study.

Abnormal Laboratory Values

A clinical laboratory abnormality that can reasonably be related to the administration of the study formulation should be documented as an adverse event.

Page 17 of 32

Hospitalization, Prolonged Hospitalization or Surgery

Hospitalization, prolonged hospitalization, or surgery is to be reported as an adverse event if it can reasonably be related to the administration of the study formulation.

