8.2 Recording of Adverse Events

At each contact with the subject, the Principal Investigator and/or Investigators must seek information on adverse events by specific questioning and, as appropriate, by examination. Information on all adverse events should be recorded immediately in the appropriate adverse event section of the Case Report Form. All clearly related signs and symptoms should be recorded.

All adverse events occurring during the study period must be recorded. The clinical course of each event should be followed until resolution, stabilization, or until it has been ultimately determined that the study treatment or participation is not the probable cause. Serious adverse events that are still ongoing at the end of the study period must be followed up, to determine the final outcome. Any serious adverse event that occurs after the study period and is considered to be at least possibly related to the study treatment or study participation will be recorded and reported immediately.

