9.1 Confidentiality

Information about study subjects will be kept confidential and managed according to the requirements of the Health Insurance Portability and Accountability Act of 1996 (HIPPA). Those regulations require a signed subject authorization informing the subject of the following:

- What protected health information (PHI) will be collected from subjects in this study
- Who will have access to that information and why
- Who will use or disclose that information
- The rights of a research subject to revoke their authorization for use of their PHI

In the event that a subject revokes authorization to collect or use PHI, the Principal Investigator and Investigators, by regulation, retain the ability to use all information collected prior to the revocation of subject authorization. For subjects that have revoked authorization to collect or use PHI, attempts will be made to obtain permission to collect at least vital status (long term survival status that the subject is alive) at the end of their scheduled study period.

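### Section 4.4 ends data collection and contact for withdrawn patients while 8.1 and 8.2 require unresolved events to be followed, and early stoppers have no post-baseline tolerability rating

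*Combined protocol and SAP*

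**What the plan says.** **Withdrawal rules.** Section 4.4.1 states: "No data will be collected for withdrawn subjects and withdrawn subjects will not be replaced. There will be no follow-up for withdrawn subjects". Section 4.4.2 adds that "no additional attempts will be made to contact the Participant". Among the pre-specified reasons, 4.4.1 lists "Adverse Event: Patient experienced a related or unrelated event that would interfere with the study objectives/evaluation" and, as a separate item, "Lost to Follow-up: Patient did not come in for a visit and could not be reached by phone". The rule on data and follow-up is the same for every reason.

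**Adverse event rules.** Section 8.1, under its paragraph on post-study events, says: "All unresolved adverse events are to be followed by the Principal Investigator and/or Investigators until the events are resolved". The other endpoints it allows are loss to follow-up and another explanation. Section 8.2 says "The clinical course of each event should be followed until resolution, stabilization", or until treatment or participation is judged not to be the probable cause. It also says "Serious adverse events that are still ongoing at the end of the study period must be followed up". The same section requires all events in the study period to be recorded, and recorded at once.

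**Tolerability endpoint.** Section 3.4 has four symptoms (itching, swelling, stinging or burning, dryness) rated 0 to 3 at the initial and final visits. The schedule in 6.6 has two visits, Week 0 and Week 2, and no early-termination visit. Section 7.2.1 reports the proportion of patients in each category and leaves missing values missing. Section 7.3 puts every treated patient in the primary analysis regardless of withdrawal.

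**The concern.** A patient withdrawn with an active skin reaction falls under both sets of rules. Section 4.4 tells the site to collect nothing more and make no contact; 8.1 and 8.2 tell it to follow the reaction. Staff cannot do both, and nothing says which governs.

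There is also a statistical cost. Tolerability is in the title, in the objectives of the Study Summary and in the Primary Hypothesis. It is rated once after baseline. A patient who stops early because the cream is not tolerated never reaches that rating, so the chance of being missing depends on the outcome being measured, and the bias favours the product. With 10 patients and no replacement, a single such patient shifts the result by about 10 percentage points.

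**Working it through.** **Step 1. Do the texts conflict?** Take a patient withdrawn before Week 2 with an unresolved reaction.

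- Further data and contact: none under 4.4.1 and 4.4.2, with no exception for adverse events.
- Follow-up of the event: required under 8.1 and 8.2, with no exception for withdrawn patients.
- The loss-to-follow-up exit in 8.1 does not reconcile them. In 4.4.1 that is a separate reason, for a patient who missed a visit and could not be reached. A patient withdrawn for an adverse event may well be reachable; 4.4.2 rules out trying.
- Nor can 8.1 be read as ending with participation, because the rule sits in the paragraph on post-study events.

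Other sections lean on the same information. Section 8.3.1 asks for the resolution of each event and its date. The stopping rule in 8.5 turns on whether dermatitis resolves. For patients who revoke authorization, 9.1 says "attempts will be made to obtain permission to collect at least vital status", which sits badly with the no-contact rule in 4.4.2.

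**Step 2. What is kept and what is lost?** An event reported before or at withdrawal should be on the case report form under 8.2. Two things are lost: the later course and outcome of an event still open at withdrawal, and the Section 3.4 rating, since the only post-baseline one is at Week 2. Section 4.4.1 does not say whether data gathered before withdrawal are kept.

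**Step 3. Size.** The plan has no figure to reproduce: 7.1 gives 10 patients without a power calculation, and no dropout rate is stated. Assumptions for illustration:

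- *k* of 10 treated patients withdraw with a severe rating, *k* = 1, 2 or 3;
- no completer has a severe rating;
- the safety denominator is patients with a Week 2 rating.

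Intervals are exact (Clopper-Pearson) 95%. For 0 of *n* the upper limit is 1 − 0.025^(1/*n*); for *n* = 8, 1 − 0.025^(1/8) = 0.369.

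| *k* | Rated at Week 2 | All treated, rating at stopping kept |
|---|---|---|
| 1 | 0/9 = 0% (0 to 33.6%) | 1/10 = 10% (0.3 to 44.5%) |
| 2 | 0/8 = 0% (0 to 36.9%) | 2/10 = 20% (2.5 to 55.6%) |
| 3 | 0/7 = 0% (0 to 41.0%) | 3/10 = 30% (6.7 to 65.2%) |

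If the denominator were instead all 10, with a row for missing, the severe count would still be 0/10. The denominator alone does not repair the loss.

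**Step 4. Does the sensitivity analysis in 7.3 help?** It excludes patients who withdrew. Those without a Week 2 rating add nothing to the severe count in either analysis. Among rated patients the two analyses therefore give the same proportion, and the comparison cannot reveal the problem.

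**Step 5. How likely is at least one such patient?** With an assumed chance *p* per patient, 1 − (1 − *p*)^10 gives 40% for *p* = 0.05, 65% for *p* = 0.10 and 89% for *p* = 0.20.

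**The case against.** A reader might infer that patients harmed by the cream vanish from the safety results altogether. The documents do not support that. Section 8.2 requires questioning about adverse events at each contact and immediate recording, so a patient who calls to stop because of a reaction should have it recorded. The record in 8.3.1 even provides for resolution after discontinuing treatment. Section 7.3 keeps treated patients in the primary analysis, and 9.1 lets information collected before a revoked authorization be used. All of this stands, and it limits the point to the rating and to the later course of open events. It does not remove the point: 7.3 cannot supply a rating that was never taken, and 9.1 speaks of revoked authorization, not of withdrawal in general.

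A reader might also take 0/8 as what the plan would report. The plan does not fix the safety denominator: 7.3 points to all treated patients, while 7.2.1 leaves missing values missing. A severe dermatitis is not the same thing as a rating of 3 on one of four symptoms, and it would also be an adverse event relevant to 8.5. The figures therefore concern one category of one table under stated assumptions.

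Two further limits are fair. Ending study follow-up is not the same as ending care, since patients come from the centre's own outpatient practice. The FDA reporting deadlines in 8.3.2 run from receipt of the information, so a first report does not wait for an outcome.

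**Conclusion.** The contradiction between 4.4 and 8.1/8.2 is real, rests on current text and needs no assumption. The adverse event record itself is not lost; the later course of unresolved events and the only post-baseline tolerability rating are.

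The direction of the bias is favourable to the product, provided that some patients stop early because of poor tolerability. Its size is not known from the documents. Under the stated assumptions the severe proportion is understated by 10 to 30 percentage points for one to three such withdrawals. In a two-week pilot of 10 patients the number may well be zero, in which case only the contradiction remains. That alone warrants correction, because it governs what staff do for a patient who leaves with an open event.

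**What to change.** Amend 4.4.1 and 4.4.2 to separate stopping the cream from withdrawing consent to contact. Unless that consent is withdrawn:

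- obtain the Section 3.4 ratings and adverse event information at the time of stopping;
- make 4.4 consistent with the adverse event follow-up that 8.1 and 8.2 already require.

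State that data collected before withdrawal are kept, and bring the no-contact sentence into line with 9.1.

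In 7.2 and 7.3, define the safety denominator. Report tolerability for all treated patients, using the Week 2 rating or, where there is none, the rating at stopping. Show Week 2 and at-stopping ratings separately as well, and give the number with neither.

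The cost is a wording amendment and one extra contact per withdrawal. The drawback is that a rating at stopping is not taken at Week 2, so the combined figure mixes time points; the separate display addresses this.

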4.4.2 Data Collection and Follow-up for Withdrawn Subjects

If a Participant withdraws from the study, no additional attempts will be made to contact the Participant.

5 Study Drug

5.1 Description

The "skin guard" study formulation is a combination of components of FDA approved drugs trolamine salicylate 10%, sodium cromolyn 5%, and diphenhydramine 1% as well as the skin moisturizer Vanicream (OTC). The components will be compounded into a cream formulation and is intended for topical application to the skin. The drug product will be packaged in a polypropylene ointment jar with screw cap lid.

5.2 Study Procedures

Preparation and Administration of Study Drug

Each participant will receive both verbal and written instructions as to proper dosing and application and storage. The Mayo Clinic Research Pharmacy in Rochester, MN will prepare, store and distribute the study formulation. Participants will receive 2-one-half pound ointment jars of the study formulation. The jars will be returned the final visit.. The returned used jars will be weighed by the Principal Investigator or a study team member to determine the amount used/compliance. Should additional cream be required during the 2 weeks of the study, the patient can contact the principal investigator or the clinical study coordinator. Upon notification from the patient, an extra ½ pound jar will be sent to the patient by overnight express mail.

Instructions will be provided as follows: Twice daily, apply a thin film of the study formulation to symptomatic areas of the skin including about one centimeter of normal appearing skin surrounding each area of involvement. Rub lightly and uniformly into the skin. An investigator will demonstrate correct application by using a bland emollient moisturizer.

Subject Compliance Monitoring

Adherence to the treatment regimen is of great importance. Poor compliance may result from lack of patient understanding, discomfort caused by the product and unrealistic expectations. Assessment of participant compliance will be determined by weighing ointment jars at the time of the final visit. Participants are not expected to use a specific amount of the study formulation . Rather, use will be individualized depending on the amount of symptomatically involved skin. Those who are non-compliant with the study protocol despite additional counseling and the opportunity to correct will be withdrawn.

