3.2 Primary Study Endpoints

Scorma Index[see below]

The proportion of participants who achieved complete resolution or near-complete clearing of cutaneous symptoms of treated, involved skin after 2 weeks' treatment will be evaluated using the SCORing MAstocytosis (SCORMA) index. SCORMA has been utilized to evaluate the severity of cutaneous mastocytosis and to correlate with serum tryptase levels. Repeated SCORMA determinations can "provide a rapid impression of changes in the clinical status" in mastocytosis (HeideR, van Doorn K, Mulder PG et al. Serum tryptase and SCORMA (SCORing MAstocytosis) index as disease severity parameters in childhood and adult cutaneous mastocytosis. Clinical and Experimental Dermatology 2008; 34: 462-468.)

The SCORMA index is calculated by the formula A/5 +5B +2C/5 where A=Extent of skin involvement,

B= Intensity (pigmentation/erythema + vesiculation + elevation + positive Darier's sign each rated 0[absent], 1[mild] 2[moderate] or 3[severe]).

C= subjective symptoms utilizing visual analog scale 1-10 of the following: provoking factor(s), flushing, diarrhea, pruritus, localized bone pain.

Since it will be impractical for patients to apply Skin Guard to the entire body surface area, and not all areas of the skin will be involved to the same extent, we will limit application to between 9% and 18% of the skin (see SCORMA figure). In this regard we will attempt, when possible, to utilize equally involved sides of the torso or extremities to facilitate evaluation of effectiveness. We will generate not only a "Global" SCORMA value, but in addition a SCORMA value for the treated, involved skin. The latter should give a more accurate estimation of the effectiveness on treated areas.

Quality of Life –SkinDex-16[see below]. Skindex-16, a validated measurement of the effects of skin diseases on patients' quality of life will be utilized to follow this parameter. SkinDex has been used and adapted for dermatologic research internationally (Chren M-M, The SkinDex instruments to measure the effects of skin disease on quality of life. Dermatology Clinics 2012; 30: 231-236).

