6.1 Visit 1 (Week 0/Baseline)

- a) Assess degree of cutaneous involvement by SCORMA Index; Indicate area(s) of the skin to be treated; generate "Global" and "Local" SCORMA values; physical exam/vital signs
- b) Obtain β -HCG. Obtain baseline levels of tryptase, urinary N-MH, LTE4, and 2,3 dinor 11 β PGF2 α if (not obtained during prior 6 months).
- c) Review medical history and current medications
- d) Informed consent
- e) Patient to complete Quality of life questionnaire-SkinDex-16.
- f) Baseline photographs
- g) Review treatment protocol
- h) Dispense study formulation

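### For patients with symptomatic skin beyond 18%, the application instruction in Section 5.2 conflicts with the treated-area limit in Section 3.2 (minor)

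*Combined protocol and SAP*

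**What the plan says.** Three parts of the combined protocol and SAP govern where the cream goes.

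- **Section 3.2 (Primary Study Endpoints)** sets a limit: "we will limit application to between 9% and 18% of the skin". The reason given is that treating the whole body is impractical and that involvement varies by site. The investigators will try to "utilize equally involved sides of the torso or extremities to facilitate evaluation of effectiveness". A SCORMA value for the treated, involved skin is generated alongside the Global value.
- **Section 6.1(a) (Visit 1)** fixes the area at baseline: "Indicate area(s) of the skin to be treated". Global and Local SCORMA values are then generated.
- **Section 5.2 (Study Procedures)** gives the instruction for patients: twice daily, "apply a thin film of the study formulation to symptomatic areas of the skin", with a margin of about one centimetre. It states no upper limit and does not refer to the area chosen at Visit 1. The compliance paragraph follows the same logic: "Participants are not expected to use a specific amount of the study formulation", and "use will be individualized depending on the amount of symptomatically involved skin". More cream is available on request ("Should additional cream be required during the 2 weeks of the study").

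**The concern.** The design assumes that a chosen part of the skin is treated and the rest is not. The instruction assumes that whatever is symptomatic is treated. For a patient with widespread symptomatic skin these are different regimens, and the protocol does not say which prevails.

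Two things are at stake. The first is exposure: treated area drives the amount applied, and the background in Section 1.1 notes that excessive absorption of topical antihistamines could have systemic effects. The second is interpretation. Global SCORMA and SkinDex-16 describe the whole patient, so their change would partly reflect how much skin that patient decided to treat. SkinDex-16 matters in particular because Section 7.2.1 joins the response criteria with and/or, so improvement in all three domains, or in two, can by itself make a patient a complete or near-complete responder.

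**Working it through.** **1. When the two rules conflict.** Let S be the percentage of skin that is symptomatic.

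- S between 9% and 18%, all of it designated at Visit 1: both rules can be followed.
- S above 18%: Section 5.2 directs cream to S%, while Section 3.2 allows at most 18%. At least S − 18 percentage points of skin are treated outside the designated area. Both rules cannot be followed.

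The documents give no distribution of S, so the number of affected patients among the 10 is unknown. Section 3.2 does anticipate involvement too extensive to treat in full.

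**2. Size of the effect on Global SCORMA.** Section 3.2 states: "The SCORMA index is calculated by the formula A/5 +5B +2C/5 where A=Extent of skin involvement". Take A as a percentage of skin (as in 7.2.1), B as the sum of four items scored 0–3 and C as the sum of five scales up to 10. The maximum is 100/5 + 5 × 12 + 2 × 50/5 = 20 + 60 + 20 = 100.

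Clearing all treated skin lowers the extent term by at most (treated %)/5. Within the limit that is 9/5 = 1.8 to 18/5 = 3.6 points. The table assumes that symptomatic skin equals involved skin, that film thickness is equal and that the one-centimetre margin is ignored. Values of S above 18% are assumptions.

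| S | Ceiling on fall in A/5 under 3.2 | Ceiling under 5.2 | Amount applied relative to 18% |
|---|---|---|---|
| 18% | 3.6 | 18/5 = 3.6 | 1.0 |
| 36% | 3.6 | 36/5 = 7.2 | 36/18 = 2.0 |
| 54% | 3.6 | 54/5 = 10.8 | 54/18 = 3.0 |
| 100% | 3.6 | 100/5 = 20 | 100/18 = 5.6 |

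**3. Responder proportion.** One patient who changes category through SkinDex-16 moves the proportion by 1/10 = 10 percentage points. That is true of anything that reclassifies one patient; it shows sensitivity and does not estimate an effect.

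**4. Whether jar weights would reveal it.** Two half-pound jars hold about 454 g. Over 2 × 14 = 28 applications that is 454/28 = about 16.2 g each, or about 24.3 g with one extra jar. The documents give no grams per percentage of skin and expect no particular amount, so weight cannot show where the cream went.

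**5. Local SCORMA.** Extent and intensity are scored on the designated skin, which is treated under either rule. Only the symptom term, which includes items such as flushing and diarrhoea that belong to no single site, could respond to treatment elsewhere. Local SCORMA is therefore largely unaffected.

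**The case against.** The strongest reply is that Section 5.2 describes how to apply the cream, within areas the investigator has already chosen. The limit in 3.2 is the investigators' to enforce. At Visit 1 they designate the area, review the treatment protocol with the patient (6.1(g)) and then dispense. Section 5.2 promises verbal and written instructions and a demonstration, and a patient handout is listed in Section 15, though its text is not visible here. Extra cream requires contact with the study team. At the end, 6.5(g) reviews compliance and the Local SCORMA form asks for the treated area.

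Much of this stands. Patients may well be told the limit, and a departure could come to light at the final visit. But none of these steps, as written, tells the patient to stay inside the designated area, and the compliance paragraph again ties use to symptomatic skin. If the handout does state the limit, it contradicts 5.2.

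A reader might infer three stronger points, which the documents do not support:

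- **That a side-to-side comparison is lost.** Section 3.2 does not say that one side stays untreated, and Section 7 plans no such analysis.
- **That the primary response is invalidated.** The SCORMA criteria in 7.2.1 refer to treated, involved skin. That SkinDex-16 can qualify a responder alone is a feature of the response definition, present however much skin is treated.
- **That there is a safety hazard.** The multiples above are of amount applied and say nothing direct about absorption. Section 3.4 expects minimal systemic absorption, and the reason 3.2 gives for the limit is practicality.

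**Conclusion.** The conflict is real, conditional and minor. Where symptomatic skin exceeds 18%, following 5.2 as written breaks the 3.2 limit and treats skin outside the Local SCORMA area. Exposure and the change in Global SCORMA and SkinDex-16 would then vary with each patient's choice of treated area.

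The ceilings of 7.2 to 20 points on the Global extent term, against 3.6 within the limit, rest on assumed involvement of 36% to 100% and complete clearing of all treated skin in two weeks. They bound the effect and do not predict it. What is established is a contradiction between two stated rules. Whether any patient would over-treat depends on involvement and on instructions that cannot be seen here.

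**What to change.** - **Section 5.2 and the patient instructions:** apply twice daily, only to the area(s) designated at Visit 1 (selected by the investigator under 3.2, at most 18% of the skin), plus about 1 cm around each lesion within that area; do not treat other symptomatic areas. Give the upper limit only. The 9% floor guides the investigator's selection, and no inclusion criterion requires 9% involvement.
- **Section 5.2, compliance paragraph:** make use depend on the amount of involved skin in the designated area.
- **Section 6.5(g):** confirm that application stayed within the designated area and note any departure.

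The cost is one clause, one amended sentence and one line under an existing step, with no added visits, patients, measurements or CRF pages. The references elsewhere to four weeks, week 4, daily use and aspirin are separate clerical corrections and add no weight to this point.

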6.5 Visit 2-Final visit (Week 2 +/- 1 day)

- a) Reassess cutaneous mastocytosis severity by (Global & Local) SCORMA Indexes; monitor vital signs
- b) Investigator Assessment of Global Improvement
- c) Quality of life assessment:SkinDex-16
- d) Review changes to medical history and current medications
- e) Review contraception (female patients of childbearing potential)
- f) Review adverse events
- g) Review compliance

- h) Repeat photographs
- i) Obtain levels of serum tryptase, urinary N-MH, LTE4, and 2,3 dinor 11β PGF2α
- j) Reconcile study formulation

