7.1 Sample Size determination

Due to the pilot nature of the study, no formal statistical power/sample size calculations are necessary. The sample size of 10 patients will be sufficient for this pilot study to obtain a preliminary estimate of treatment efficacy and to generate data that will be useful in the design of a larger study.

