7.2.1 Definition of response

Complete response:

Clinically significant SCORMA improvement in all 3 parameters of treated, involved skin: % skin involvement; activity or symptoms &/or

Improvement in all 3 SkinDex-16 domains (Emotions, symptoms, functioning) &/or Resolution of 75% of cutaneous lesions

Near Complete response:

Clinically significant SCORMA improvement in two of 3 parameters of treated, involved skin: % skin involvement; activity or symptoms and/or

Improvement in 2 SkinDex-16 domains (Emotions, symptoms, functioning) &/or Resolution of >50% of cutaneous lesions

Partial Response:

Clinically significant SCORMA improvement in one 3 parameters of treated, involved skin: % skin involvement; activity or symptoms and/or

Improvement in 1 SkinDex-16 domain (Emotions, symptoms, or functioning) &/or Resolution of >25% of cutaneous lesions

No response:

No significant SCORMA improvement in any of 3 parameters of treated, involved skin: % skin involvement; activity or symptoms and/or

Improvement in no SkinDex-16 domain (Emotions, symptoms, functioning) &/or Resolution of no cutaneous lesions.

*Additionally, for primary safety endpoints which will be scored as none, mild, moderate, or severe, the proportion of patients in each category at each follow-up time point will be estimated for each of the different safety endpoints. P-values of 0.05 or lower will be considered as statistically significant.

Handling of missing data

This is a prospective study and therefore we do not anticipate any missing data. In the event of any unexpected missing data, no attempt to impute this missing data will be made; missing data will simply be treated as missing in the statistical analysis.

Multiplicity

Since this is an exploratory pilot study, no adjustment for multiple testing is needed. P-value of 0.05 or lower will be considered as statistically significant.

Primary Hypothesis:

The study seeks to demonstrate the effectiveness and tolerability of a novel topical composition consisting of 3 components (diphenhydramine, aspirin and cromolyn sodium) in a neutral skin moisturizing cream (Vanicream) for the treatment of cutaneous lesions of mastocytosis. This will be determined by the proportion of participants who achieve complete or near-complete response utilizing the SCORMA Index, and SkinDex-16 QOL.

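### Withdrawal for non-compliance or treatment failure is related to outcome, and a patient withdrawn before Visit 2 leaves no week-2 response or tolerability rating for the all-treated analysis to use

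*Combined protocol and SAP*

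**What the plan says.** **Withdrawal.** Section 5.2 requires it for persistent non-compliance: "Those who are non-compliant with the study protocol despite additional counseling and the opportunity to correct will be withdrawn". The same paragraph gives the causes it expects: "Poor compliance may result from lack of patient understanding, discomfort caused by the product and unrealistic expectations". Section 4.4.1 lists further reasons, among them treatment failure, meaning that the Principal Investigator judges that the patient's "condition required another form of treatment".

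**How compliance is judged.** "Assessment of participant compliance will be determined by weighing ointment jars at the time of the final visit". There is no threshold: "Participants are not expected to use a specific amount of the study formulation". The schedule in 6.6 has two visits, at weeks 0 and 2. At Visit 2 (6.5), SCORMA scoring is item a and "Review compliance" is item g. The study is open-label (5.5).

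**What happens to withdrawn subjects.** Nothing is collected from them, they are not replaced and they are not followed (4.4.1). No further contact is attempted (4.4.2).

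**Analysis.** Section 7.3 puts everyone who received study drug in the primary analysis, whatever the reason for withdrawal. It confines exclusion of withdrawals to a secondary sensitivity analysis. Section 7.2.1 does not impute missing values and has no rule that counts a missing outcome as non-response.

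**The concern.** Two of the listed reasons for withdrawal are close to the endpoints themselves. Discomfort from the cream is what the tolerability ratings in 3.4 measure (itching, swelling, stinging or burning, dryness). Treatment failure is close to non-response. An unmasked investigator applies both, without a defined threshold for compliance.

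If such a patient leaves before Visit 2, the data rules ensure that no week-2 observation exists. The remaining patients are then a favourable selection for both the response proportion and the tolerability table. The study has ten patients, no control arm and no replacement, so nothing in the design offsets the loss. Section 7.1 intends the result to inform a larger study, so an inflated estimate would carry forward.

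**Working it through.** **Step 1: follow a withdrawn patient through the rules.**

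| Time of withdrawal | Week-2 data | Primary analysis (7.3) | Secondary analysis (7.3) |
|---|---|---|---|
| Before Visit 2 | None (4.4.1, 4.4.2); not imputed (7.2.1) | Included in name, but no value to analyse | Excluded |
| At Visit 2, after scoring | Exists; 4.4.1 does not say whether it is kept | Included, if the score is kept | Excluded |

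The first row is where selection arises.

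**Step 2: can the compliance rule operate as written?** It requires counselling and a chance to correct before withdrawal. Jars are weighed only at the second of two visits, so no scheduled contact lies between detection and the end of the study. The other non-compliance trigger in 4.4.1, two consecutive missed visits, does not fit either, because a treated patient has only one visit left to miss. In practice the rule rests on discretion.

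**Step 3: size for the response proportion.** The plan gives no power, effect size or dropout rate, so there is no figure to reproduce. The sample size is 10 (7.1). Assumptions: 3 to 5 true responders; k = 1 to 3 patients withdrawn before Visit 2, all non-responders. Observed proportion = responders/(10 − k).

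| True responders | k = 0 | k = 1 | k = 2 | k = 3 |
|---|---|---|---|---|
| 3 | 3/10 = 30% | 3/9 = 33% | 3/8 = 38% | 3/7 = 43% |
| 4 | 4/10 = 40% | 4/9 = 44% | 4/8 = 50% | 4/7 = 57% |
| 5 | 5/10 = 50% | 5/9 = 56% | 5/8 = 63% | 5/7 = 71% |

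Exact (Clopper-Pearson) 95% intervals are 19% to 81% for 5/10 and 25% to 91% for 5/8. The shift is smaller than the sampling uncertainty, but it always goes in the cream's favour under these assumptions.

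**Step 4: size for tolerability.** Assume 2 of 10 patients have stinging, both withdraw before the week-2 rating and nobody else is affected. The table then shows 0/8 = 0% instead of 2/10 = 20%.

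**Step 5: size for the paired test.** Section 7.2.1 uses a Wilcoxon signed rank test, with "P-value of 0.05 or lower will be considered as statistically significant". Sidedness is not stated, so two-sided is assumed. A simulation of 20,000 trials used normally distributed changes with no true effect, removed the k worst of 10 and applied the exact test. The type I error was 4.6% for k = 0, then about 8%, 17% and 31% for k = 1, 2 and 3. This is an upper bound in spirit, since withdrawals need not be the worst outcomes.

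**The case against.** The strongest reply is section 7.3. It keeps every treated participant in the primary analysis, so a patient scored at Visit 2 and then called non-compliant stays in. That stands. The figures above do not apply to such a patient in the primary analysis.

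A reader might infer more: that the investigator can see a poor week-2 score, then label the patient non-compliant and remove the result. The documents do not support this, for three reasons.

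- Section 7.3 blocks that route in the primary analysis.
- The idea that compliance is judged after scoring rests only on list order in 6.5. The visit lists are not chronological: Visit 1 (6.1) puts SCORMA first and informed consent fourth, although section 11 requires consent before any study procedure. All that can be said is that both happen at the same visit.
- The rule in 5.2 requires counselling and a chance to correct, which non-compliance first found at the last visit could not properly satisfy.

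Two further objections stand in part. The compliance rule does not mention response, so non-responders are reached mainly through the separate treatment-failure reason. And 8.2 requires all adverse events during the study period to be recorded, with questioning at each contact, so stinging should still appear as an adverse event if there is contact. The week-2 rating would still be lost.

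What 7.3 cannot do is supply an outcome that was never collected. It also does not say whether scores already taken are kept, and its own secondary analysis drops withdrawn patients.

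**Conclusion.** The concern holds for patients withdrawn before Visit 2. Outcome-related reasons for withdrawal, combined with no data, no contact, no imputation and no non-responder rule, can bias both the response proportion and the tolerability table in the cream's favour. With 5 true responders and one or two non-responders lost, the response proportion rises by 6 or 13 percentage points (56% − 50%; 62.5% − 50% = 12.5). The tolerability example moves from 20% to 0%.

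These counts are assumed, and the loss is taken as the worst case. If no patient is withdrawn before Visit 2 and scores already taken are kept, the primary analysis has no such bias. The point should be corrected because the study is meant to inform a larger one, but it does not undermine the pilot by itself.

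**What to change.** Amend 4.4.1, 4.4.2 and 5.2 so that stopping the cream is distinct from leaving the study:

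- Record non-compliance and treatment failure as a protocol deviation or a reason for stopping the cream, not as withdrawal from the study. Whether the cream is continued remains a clinical decision.
- Keep all Visit 2 assessments for every treated patient who has not withdrawn consent.
- Limit the no-data and no-contact wording to patients who withdraw consent. Otherwise, withdrawals for adverse events would still lose their week-2 data.
- State that data already collected are kept.
- Reconcile 7.2.1 with 7.3 by counting a treated patient without a week-2 outcome as a non-responder in the response proportion.
- Reconcile the counselling step in 5.2 with the two-visit schedule, and say how non-compliance is judged. The investigators should settle how.

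The cost is a wording amendment, since Visit 2 is already scheduled. The downside is that the response proportion may be slightly lower, because it includes patients who used little cream. The non-responder rule is also conservative: if one of 5 true responders leaves without an outcome, the result is 4/10 = 40% instead of 50%.
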